## Examination of First and Second Generation E-cigarettes

### Abstract

The 2009 Family Smoking Prevention and Tobacco Control Act grants the FDA regulatory authority over tobacco-based products. However, the FDA only recently proposed deeming regulations on e-cigarettes. Since their market emergence, e-cigarettes have evolved from first generation products, which look like a conventional cigarette, have few design components and limited nicotine delivery, to second generation products, which do not look like conventional cigarettes, have multiple design components and can achieve cigarette-like levels of nicotine-delivery. Missing from the current literature is a prospective study assessing differences between these two major types of e-cigarettes on smoking behaviors and patterns, nicotine dependence, and on biomarkers of toxicant exposure and effect. Understanding the differential impact of first versus second generation e-cigarettes on smoking as well as measures of proximal health outcomes will help immediately inform the science base needed for the FDA to impose appropriate product specific regulations. The overall aim of the proposed study is to evaluate the effect of switching from conventional cigarettes to either a first or second generation e-cigarette on smoking behavior, product use patterns and continued use, as well as biomarkers of toxicant exposure and effects. To do so, we will randomly assign 453 adult smokers, naïve to e-cigarette use, to low-wattage devices (LWD), high-wattage devices (HWD), or usual brand cigarette control (UBC). All products will be provided for 12 weeks. Enrollment will be restricted only to smokers not planning to quit in the next 3 months. Prior to randomization, all participants will take part in a lead-in period to assess normal smoking behavior and to allow for stratification on important variables. Follow-ups will occur at 1, 4, 8, 12, 26, and 52 weeks. Our specific aims are to 1) assess the effect of provision of LWD vs. HWD on product switching, abuse liability, number of cigarettes smoked, and perceived nicotine dependence; 2) evaluate changes in biomarkers of harmful tobacco constituent exposure among participants assigned to LWD, HWD, and UBC; and 3) evaluate changes in biomarkers of toxicant effect among participants assigned to LWD, HWD, and UBC. This innovative study in its comprehensive examination of all e-cigarette devices as well as their impact on smoking behavior and health outcomes, will provide the scientific foundation the FDA and other agencies need to establish effective regulatory strategies for the manufacture, distribution, and marketing of e-cigarettes.

### Project Narrative/relevance to public health

E-cigarettes are proliferating and evolving rapidly in the current unregulated market. To date, it is not clear how e-cigarette products in general will impact smoking behavior and downstream health outcomes, let alone the differential effects between first versus second generation e-cigarette products. The proposed work will prospectively examine the effect of switching to e-cigarettes on changes in smoking patterns, nicotine dependence, exposures to harmful toxicants, and downstream physiological health effects.

### Potential Benefits of the Proposed Research

Whereas no assurance can be made to an individual participant that he/she will personally benefit from this research, the experience should be beneficial. All participants will be encouraged to quit smoking at the completion of the study and will be provided referrals to local cessation resources. Adequate protections are in place in the event of unlikely and mild risks for study participation. Overall, it is expected that the potential benefits to participants in the proposed study outweigh the potential risks.

## Examination of First and Second Generation E-cigarettes

### A. Specific Aims

The 2009 Family Smoking Prevention and Tobacco Control Act granted the FDA's Center for Tobacco Products regulatory authority over tobacco-based products. However, the FDA only recently proposed deeming regulations on e-cigarettes (ECs). Since their market emergence, ECs have evolved from low-wattage devices (LWD) which look like conventional cigarettes, have few design components and limited nicotine delivery, to high-wattage devices (HWD) which do not look like conventional cigarettes, have multiple design components and can achieve cigarette-like levels of nicotine-delivery. Each step of the evolution has led to increased consumer momentum, as well as increased demand from health officials to establish a science base to answer the question, "Are e-cigarettes a benefit or burden to public health?"

Our own as well as others' research is beginning to suggest that very few exclusive EC users use LWD products. However, for a majority of current HWD users, a LWD product was the first vapor-based product they tried. In other words, the limited available data suggests that LWDs may lead to dual use and/or serve as a gateway product to HWD products. HWD products, on the other hand, appear to be sufficient for some smokers for exclusive use—likely due, at least in part, to better nicotine delivery. Conversely, better nicotine delivery may also lead to continued long-term nicotine addiction. Moreover, HWDs may also yield more toxic and carcinogenic compounds per puff than LWDs due to higher heating of the vapor. Missing from the current literature is a prospective study assessing differences between these two major types of ECs on smoking behaviors and patterns, nicotine addiction, and on biomarkers of toxicant exposure and effect. Understanding the differential impact of LWD vs. HWD products on smoking as well as measures of proximal health outcomes will help immediately inform the science base needed for the FDA to impose appropriate product specific regulations.

**The overall aim of the proposed study is to evaluate the effect of switching from conventional cigarette smoking to one of two types of ECs on smoking behavior, product use patterns and continued use, as well as biomarkers of toxicant exposure and effects.**

To do so, we will randomly assign 453 adult smokers, naïve to EC use, to LWD electronic cigarette; b) HWD electronic cigarette; or c) usual brand cigarette control (UBC). All products will be provided at no cost to the participant for 3 months. Enrollment will be restricted only to smokers not planning to quit in the next 3 months. Prior to randomization, all participants will take part in a lead-in period to assess normal smoking behavior and to allow for stratification on important variables.

#### Aim 1:

**To assess the effect of provision of LWD vs. HWD on product switching/substitution, abuse liability, number of cigarettes smoked, and perceived nicotine dependence.** *Hypothesis 1a: Complete product substitution (vs. partial or no substitution) will occur at a significantly higher rate among smokers randomized to HWD products compared to those randomized to LWDs at 12, 26, and 52-week follow-ups. Hypothesis 1b: Compared to those randomized to UBC, LWD and HWD participants will smoke fewer cigarettes per day, have lower product abuse liability and lower perceived nicotine dependence.*

**Aim 2: To evaluate changes in biomarkers of harmful tobacco constituent exposure among participants assigned to LWD, HWD, and UBC.** *Hypothesis 2a: The degree of changes in exposure will be directly associated with the degree of substitution with EC—greater levels of substitution will confer a larger decrease in exposure to harmful constituents. Hypothesis 2b: Among those who completely substitute ECs for conventional cigarettes, LWD users (vs. HWD) will have significantly lower levels of biomarkers of exposure.*

## Examination of First and Second Generation E-cigarettes

**Aim 3: To evaluate changes in biomarkers of toxicant effect among participants assigned to G1, G2, and UBC.** *Hypothesis 3a: The degree of changes in biomarkers of effect (levels of DNA damage-markers indicative of increased cancer risk) will be directly associated with the degree of substitution—greater levels of substitution will confer a larger reduction in levels of DNA damage. Hypothesis 3b: Among those who completely substitute ECs for conventional cigarettes, LWD users (vs. HWD) will have significantly reduced markers indicative of increased cancer risk.*

***Our team is uniquely suited to conduct this investigation. Understanding how smokers use ECs as they transition away from smoking and carefully examining their health effects is critically important. This novel study will contribute knowledge urgently needed by the FDA and health officials to effectively regulate ECs in a way that best serves public health.***

## B. Significance

### The U.S. FDA and E-cigarettes

The passage of the 2009 Family Smoking Prevention and Tobacco Control Act (FSPTCA) grants the FDA Center for Tobacco Products (CTP) regulatory authority over cigarettes, cigarette tobacco, smokeless tobacco, and roll your own tobacco. This promising piece of legislation empowers the FDA to regulate the manufacturing, marketing, and distribution of tobacco products in order to reduce tobacco-related morbidity and mortality. E-cigarettes (ECs) do not currently fall under the FDA's regulatory authority; however, in April 2014, the FDA proposed deeming regulations of ECs as well as a call for additional scientific research to inform the development of effective EC regulation. The proposed regulations 1) ban the sale of ECs to minors, 2) ban vending machine sales, 3) require warnings that ECs contain nicotine, 5) require disclosure of ingredients, and 6) prohibit distribution of free samples but with exemptions for research purposes. These regulations are important first steps in effectively regulating ECs.

### Innovation

No study has directly compared LWD vs. HWD in a prospective, long-term, randomized controlled trial. This study will break new ground and provide a rich data source for the FDA, other regulators and scientists to firmly understand the effect of EC use on both behavioral and health outcomes. Our study does not make the mistake of viewing all ECs as the same. Randomized controlled trials have almost exclusively examined LWDs and have found only modest effects on smoking behavior, while the majority of survey studies include a large portion of individuals using HWDs and generally find astounding effects on smoking behavior. Is this difference simply due to self-selection bias involved in the convenience sampling of survey studies and increased veracity of reporting in controlled trials, or are there truly differences? We believe there is a difference—some positive (higher probability of exclusive vs. dual use) and some negative (greater exposure to harmful and potentially harmful constituents and increased risk of continued nicotine dependence)—our study will be the first to directly evaluate these hypotheses.

The proposed study will also provide our team with enough time (12-months) to examine how EC use evolves: For those who slowly reduce their number of cigarettes per day, do they ever become exclusive users? Do those who become exclusive EC users stay exclusive? Do they move on to newer generation products? What is the time course for this evolution? Do they change from tobacco-flavors to non-tobacco flavors? Would they continue to use ECs if only tobacco flavors were allowed? What happens to their interest in one day quitting all nicotine? Our study will be the first to comprehensively examine these changes across the entire spectrum of EC products.

## Examination of First and Second Generation E-cigarettes

Our study will conduct the most comprehensive examination of changes in levels of cigarette and EC-related toxicants of exposure and how these levels vary between LWD vs. HWD users. We will examine exposure to tobacco-specific nitrosamines (TSNA), aldehydes, nicotine, and CO. Our study will also be the first to examine changes in the effect of toxicant exposure, specifically DNA damage (a biomarker for increased cancer risk), with a recently established and more sensitive measure of DNA analysis than any other used in previous tobacco research (PADDA, developed by [name]); changes in lung functioning will be a secondary health outcome.

Overall, this innovative study in its comprehensive examination of all EC devices and measurement of behavioral and health outcomes, will provide the scientific foundation the FDA and other agencies need to establish effective regulatory strategies.

## D. Research Design and Methods

### Design Overview

We propose to conduct a three-arm, randomized, parallel group trial that will proceed in four phases over 12 months. Participants will access the screening questionnaire using a public survey link generated by REDCap. The survey link will be distributed on Facebook posts and ads, recruitment flyers and through OSU email distribution lists. During Baseline Phase 1 (-1), participants will attend an orientation and assessment visit and be asked to smoke their usual brand of cigarettes for 1 week. During Baseline Phase 2 (0), participants will be randomized to either LWD, HWD, or usual brand cigarette control (UBC). The LWD device provided will be an eCom-BT and the HWD device provided will be an Evolv DNA 250. At this visit, those randomized to an EC group will also be able to sample EC flavors and choose their preferred flavor for the next phase of the study. The Randomized Product Trial Phase (1-12) will last 12 weeks and smokers will be asked to attempt to completely switch to the product for the next 12 weeks; otherwise, directions for use will be ad libitum. Those randomized to UBC will be instructed to use the product ad libitum. All products, to which participants will be randomized, will be provided at no cost; UBCs will be provided based on the average amount used per week collected during baseline phase 1. The Surveillance Phase will last 40 weeks, during which time no product will be provided, only assessment of continued product use (or not) and other outcomes of interest (see Table 3), as well as biomarkers of toxicant exposure and effects will be measured. Over the course of the study, all participants will complete 8 study visits: -1, 0, +1, +4, +8, +12, +26, +52 weeks. Time points for study visits were based on matching other switching studies in the literature in terms of 12-week product provision and 40-week surveillance period to allow sufficient time to examine any potential transitions. Study visits will include completion of computerized surveys and collection of specimens for biomarker analysis. Participants will also be asked to

## Examination of First and Second Generation E-cigarettes

complete a brief (<2 minute) daily online smoking/product diary into a secure database via REDCap for the 12 weeks of product provision and for the week prior to the 26- and 52-week visits.

## Study Procedures

### Participants

Cigarette smokers will be recruited from advertisements through a variety of media outlets and the internet, including Study Search, as well as community events. Participants from other studies who have agreed to be contacted regarding other study opportunities will also be contacted. Staff from those studies will prepare contact letters/emails and call participants on behalf of this study. Participants interested will be referred to this study for screening. Though we will not oversample participants of any particular background, we will advertise across a variety of media to increase the likelihood of recruitment across a range of races, ethnicities, age, socioeconomic status and locations (rural/urban). Smokers will be able to complete an online screener questionnaire generated from a secure database to determine eligibility.

Participants who meet the following eligibility criteria will be contacted by phone and asked to attend the first baseline visit. Inclusion criteria: 1) smoke  $\geq 5$  cigarettes per day for the past year; 2) not currently engaged in a quit attempt ; 3) read, write, and speak in English; 4) report at least minimal interest in switching to an alternative product ( $>$  "not at all" on a Likert scale); 5) have not regularly used a tank system, mechanical mod, or advanced personal vaporizer EC, though previous use of cig-a-like devices of 10 or less days in the last month will be allowed; 6) plan to live in the local area for next year; 7) have access to a smart phone; 8) have access to email and 9) be 21 years of age or older. Exclusion Criteria: 1)  $< 21$  years old 2) unstable or significant medical condition such as respiratory, kidney, or liver disease that could potentially affect biomarker data; 3) unstable or significant psychiatric conditions (past and stable conditions will be allowed); 4) history of cardiac event or distress within the past 3 months; 5) currently pregnant, planning to become pregnant, or breastfeeding (pregnancy and breastfeeding status will continue to be evaluated throughout the study at each visit); and 6) do not reside in the same household as a participant currently active (have not completed all study visits) in the study. If a participant is ineligible for the study at the time of screening, the participant can be reassessed at a later time to determine if they are now eligible i.e. A participant meets all other eligibility criteria, but is not eligible because they are currently pregnant or breastfeeding. The participant can submit a new screener after they are no longer pregnant or breastfeeding and can be reassessed for eligibility. Reassessment for eligibility will vary based on previous ineligibility criteria and will be determined on a participant by participant basis.

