#### **Detailed Study Procedures**

Advertisements will direct interested potential participants to complete a secure, online screener. Information regarding eligibility and the participants' email addresses and phone numbers will be uploaded into a secure database. Potential participants will then be further screened by phone.

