## Examination of First and Second Generation E-cigarettes

**Phone Screening:** Trained staff will provide a brief description of the study and for those still interested, schedule an orientation and assessment visit and provide directions to the study site. No cost ride services through Lyft will be discussed as an option for participants who may not have reliable means of transportation.

**Orientation and Assessment Visit:** During this first visit, participants will be informed of the study procedures and rationale and asked to provide informed consent. To ensure eligibility, participant smoking status will be biochemically confirmed via exhaled carbon monoxide testing ( $CO \geq 4$  ppm) and eligibility related questions will be asked again and responses verified. Pregnancy exclusion will also be confirmed with a urine test (n.b., pregnancy tests will be completed at each visit throughout the study). Participants will provide basic demographic and smoking history information consistent with questions used in the Tobacco Use Supplement to the 2006 Current Population Survey and PATH study as well as additional standardized assessment questionnaires as described below and in Table 3. Participants will be instructed to smoke as usual until their Baseline 0 visit.

**Baseline Phase 1 (usual brand cigarette):** During this baseline period (1-3 weeks), we will collect online daily smoking diaries. Upon the participant's visit to the clinic after 1-3 weeks of usual use, we will collect additional subjective measures of use as well as collection of urine, blood, saliva, and oral cells for biomarker analysis; thus, we will establish participants' baseline smoking behavior in this phase.

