## **G. Human Participants**

### **Potential Risks**

The research protocol calls for current smokers who do not plan to quit smoking within the next three months to attempt to completely substitute a LWD e-cigarette, a HWD e-cigarette, or to continue to smoke their usual brand of cigarette as they wish. Participants will not be provided any more instructions for use, and non-use of e-cigarettes is a permissible outcome. E-cigarettes are no more harmful than conventional cigarettes, and there is some evidence that they may offer reduced harm. Questionnaires, exhaled breath and urine collection procedures are all non-invasive and involve minimal risk to study participants. Potential risks are as follows: a) risk of using e-cigarettes, b) dual use of cigarettes and e-cigarettes, c) loss of confidentiality or privacy, d) potential for undermining smoking cessation, e) lack of appropriate storage of nicotine-containing products in a house with children and pets, f) slight risk of discomfort, bruising and infection with blood draw, and g) slight risk of discomfort and very low risk of infection with oral (buccal) cell collection.

The Centers for Disease Control and Prevention (CDC), the Food and Drug Administration (FDA) and several states, and federal health departments are investigating a multi-state outbreak of severe lung disease associated with using e-cigarette/vaping products. The investigation is ongoing and has not identified a cause, but all cases have reported use of vaping devices. The majority of patients have reported vaping cannabis oil,

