4. Potential for Undermining Cessation: The study sample is comprised of smokers with no plan to quit in the next three months. Therefore, we are not asking smokers who want to quit to continue smoking. Moreover, our previous study of e-cigarette sampling and use among smokers unmotivated to quit smoking suggested that e-cigarette use increased smokers' readiness and confidence to quit smoking. At the end of the study, all participants will be debriefed and educated about ECs and conventional cigarettes. This education will include the information that: a) there is no safe cigarette, b) the best thing a smoker can do to improve health is to quit, c) some ECs are manufactured by the tobacco industry, d) ECs, though able to be regulated by the FDA as a tobacco product, are currently unregulated by the FDA until they are able to develop appropriate guidelines (based on research such as the present proposal), and e) it is unclear whether ECs reduce the risks associated with smoking. The PI will be available for any questions that participants may have about ECs, smoking, or smoking cessation. It is important to note that the use of ECs incurs no greater harm than if the participant decided on his/her own to use the product. ECs are available online and over-the-counter at various convenience stores, e-cigarette specialty stores and places where tobacco products are sold. Among those screened and ineligible/uninterested, referral resources for smoking cessation will be provided for those who inquire. Among study participants, information on cessation resources will be provided at the final visit and if at any time during the study participants are interested in smoking cessation services, a list of smoking cessation resources will be provided.
5. Lack of Appropriate Storage of EC Products: Consistent with [name] previous EC studies, participants will be instructed to keep their UBCs, EC cartridges and childproof e-liquid refill containers up and away from their children and pets to protect against unintentional poisoning. Although overdose or accidental ingestion is very unlikely and has not occurred in [name] previous studies, all participants will be provided the state and national poison control telephone line as well as a "tip sheet" on recognizing signs of nicotine overdose. It is important to note that in the

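### The eligibility list bars only a current quit attempt and omits the no-plan-to-quit restriction that the protocol states elsewhere and relies on to protect participants

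*Combined protocol and SAP*

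**What the plan says.** The restriction is stated as a rule in the Abstract: "Enrollment will be restricted only to smokers not planning to quit in the next 3 months". The same sentence appears in A. Specific Aims. Section G, Potential Risks, describes those who take part as "current smokers who do not plan to quit smoking within the next three months". Section G, Protections Against Risk, item 4, states it as a fact about the sample, "The study sample is comprised of smokers with no plan to quit in the next three months", and draws a conclusion from it: "Therefore, we are not asking smokers who want to quit to continue smoking".

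The eligibility criteria are listed once, in section D under Participants. The only item on quitting is inclusion 2, "not currently engaged in a quit attempt". Section G, Recruitment and Informed Consent, says that screening follows the inclusion and exclusion criteria.

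Two later steps come before randomisation. Detailed Study Procedures says "Potential participants will then be further screened by phone", and the Phone Screening paragraph describes that call: "Trained staff will provide a brief description of the study and for those still interested, schedule an orientation and assessment visit", together with directions to the site and ride services. At the Orientation and Assessment Visit the eligibility questions are repeated.

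**The concern.** Making a quit attempt now and planning one within three months are different states. A list that bars only the first admits people whom the Abstract, the Specific Aims and section G say are not in the trial.

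Two things are at stake. The first is the participant-protection argument. Potential Risks names the undermining of cessation as a risk of the study, and item 4 of Protections Against Risk answers it by inference from the restriction. If the operative list does not contain the restriction, the inference loses its premise. Under the list as written, a smoker with a near-term quit plan could be assigned to the usual-brand arm and receive free cigarettes for 12 weeks in an amount matched to baseline use (Randomized Product Trial Phase). The second is the description of the population: a report could claim a sample without quit plans when the entry criteria do not ensure one.

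**Working it through.** The main check is a comparison of sections.

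1. **Where the restriction is stated.** It appears in four places: Abstract, Specific Aims, Potential Risks, and Protections Against Risk item 4. The first two are the same sentence, so there are three separate formulations.

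2. **What the list contains.** Inclusion items: 9. Exclusion items: 6. Total: 9 + 6 = 15, or 14 distinct, because age is given as both inclusion 9 and exclusion 1. Items on a current quit attempt: 1. Items on quit plans: 0. Inclusion 4 asks for some interest in switching products, which does not settle whether the smoker plans to quit.

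3. **Test case.** Take a smoker of at least 5 cigarettes a day who meets all other criteria, is not in a quit attempt, and plans to quit next month. Participants list: eligible. Abstract and Specific Aims: not eligible. Potential Risks and Protections Against Risk: not in the described sample.

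4. **Does a later step close the gap?** The phone call as described has no quit-plan question. The first visit repeats the eligibility questions, and the consent section refers back to the listed criteria. The Motivation Rulers (Outcome Measures; Table 3, from week -1) do ask about quitting, but they are outcome measures and not an entry check. No described step applies the restriction.

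5. **Does the sample size depend on it?** The Power Analysis assumes 15% versus 30% complete substitution, two-sided 0.05, about 80% power and 20% attrition. With pooled variance and no continuity correction, and a mean rate of (0.15 + 0.30)/2 = 0.225:

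   n per arm = [1.96 × √(2 × 0.225 × 0.775) + 0.842 × √(0.15 × 0.85 + 0.30 × 0.70)]² / 0.15² = (1.157 + 0.489)² / 0.0225 ≈ 120.5, rounded up to 121.

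   Allowing for attrition, 121 / 0.80 = 151.25, which is 152 per arm and 456 in total if rounded up, against the stated 151 and 453. Power at 121 per arm is 80.2%. The plan's figure is reproduced to within rounding, and quit intention is not an input to the formula.

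6. **Illustration only.** Suppose a share q of those enrolled plan to quit and have the 21.5% low-wattage rate that the Power Analysis cites. The low-wattage rate is then 0.15(1 − q) + 0.215q. At 121 per arm:
   - With the high-wattage rate fixed at 30%, power is 76% for q = 10%, 69% for q = 25%, 57% for q = 50% and 33% for q = 100%.
   - With the 15-point difference kept, power is 79%, 78%, 76% and 73%.
   - If all were such smokers and the high-wattage rate were also twice as high (21.5% versus 43%), power would be 95%.

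   Neither q nor the high-wattage rate in such smokers is in the documents, so even the direction of any change in power is not determined.

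**The case against.** The strongest reply is that the list is silent and not contradictory. Nothing in it permits smokers with quit plans, the Abstract and Specific Aims state the rule outright, and both can be followed together. The phone screen may apply the restriction, and a short summary of a call need not name every question. It is fair that the screener and script cannot be seen. A reader might infer that smokers planning to quit were in fact enrolled; the documents do not show that. But the suggestion that an unseen question applies the rule has no support either: the call is described without one, and screening is said to follow the listed criteria.

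The second reply is that the harm is limited. Use in the usual-brand arm is ad libitum, the other two arms are asked to switch away from cigarettes, and Protections Against Risk item 4 adds that "if at any time during the study participants are interested in smoking cessation services, a list of smoking cessation resources will be provided". All of this stands and softens the consequence. It does not restore the premise on which item 4 rests.

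The third reply is that adding the restriction now has a cost of its own. The Recruitment section reports 220 participants already recruited in Oklahoma and 233 still to come from Columbus (220 + 233 = 453). If the restriction was not applied to the first group, eligibility would then differ by site and period, and site is not among the stated stratification factors. This stands and belongs in the decision.

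**Conclusion.** The mismatch is certain on the text: the restriction is stated in four places and in none of the 15 listed criteria. Followed as written, the list admits smokers whom the protocol says it excludes and removes the support for its own safeguard. It should be corrected, at little cost. The number of participants affected is unknown and cannot be estimated from the documents.

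Two stronger conclusions might be drawn, and neither is supported. The first is that the trial is underpowered. The Power Analysis lowers the low-wattage rate from 21.5% to 15% because the reference smokers were motivated to quit, had set a quit date and received counselling. That difference cannot be assigned to quit intention alone, and the illustration above depends on figures the documents do not give. The second is that the comparison of low-wattage with high-wattage devices is biased. A quit plan held at entry precedes randomisation, so an imprecise entry rule changes who is studied without by itself favouring an arm.

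The conclusion assumes that the Participants list is the operative one, as the consent section indicates.

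**What to change.** Reconcile the Abstract, Specific Aims, Participants, Potential Risks and Protections Against Risk item 4 in one of two ways:

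- carry the stated quit-intention restriction into the Participants list and the screener, for those still to be enrolled; or
- revise the stated population and the item 4 protection so that they match the list.

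The documents do not settle which wording governs, so the sponsor has to decide and say so.

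Whichever is chosen, report baseline quit readiness from the Motivation Rulers by arm and by recruitment site and period. The rulers are already scheduled from week -1. They are an imperfect proxy, since they rate importance, confidence and readiness and are described without a three-month time frame.

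The cost is one wording amendment, one screener item under the first option, and one descriptive table from data already collected. Under the first option recruitment may slow slightly. If the restriction was not applied to the 220 already recruited, eligibility will also differ by site and period, and the report should say so. The planned comparison of low-wattage with high-wattage devices is unchanged.

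A minor wording note for the same amendment: the Abstract and Specific Aims call participants naïve to e-cigarettes, while inclusion 5 allows cig-a-like use on up to 10 days in the last month and bars only regular use of tank, mod or advanced devices. The label should match the history that inclusion 5 allows.
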